## 2 Objectives and Endpoints

### 2.1 General considerations, overview

The main objective of the trial is, whether EYT and Tai Chi can interrupt the vicious circle of chronic disease, falls, inactivity, loss of independence, reduced quality of life (see section 1.1). The primary question thereby is, whether EYT (and Tai Chi) can reduce risk of falling (fallers), which often mark the beginning of dependency and decline of mobility. Since about 50% of the patients are expected to fall with standard care, this is considered the mainly relevant endpoint and therefore chosen as primary. The number of falls is chosen as secondary endpoint. – The next important question is, whether EYT (and Tai Chi) can improve mobility and balance and reduce injuries through falls and fear of falling, which are often the primary threat to mobility. The BBS, number of injurious falls and falls efficacy scale assesses these as secondary outcome parameters.

The next question is, whether this leads to better management of daily tasks, which will be assessed by the IADL. As the overall objective is better coping with chronic disease, enabling healthy aging despite chronic disease, the next questions refers to changes in health related quality of life, cognition and mood. These are assessed with SF-12, MoCA and GDS-15. FIMA will be used to estimate an impact on health-care utilization. This will also enable economic evaluations. Finally, the ICPH will assess in how far the patients identify with their intervention.

**Objectives and related endpoints** (assessed at month 0, 3, 6, 12 after handing out the study book)

	Objective	Endpoint
Primary	Can EYT and Tai Chi reduce risk of falling within 6 months?	Risk of falling: incidence of experiencing at least one fall within 6 months (“fallers”)
Secondary	Can EYT and Tai Chi 
 
1. reduce the risk of falling within 12 months?
 
2. reduce the numbers of falls?
 
3. reduce the injuries through falling?
 
4. reduce fear of falling?
 
5. improve mobility and balance?
 
6. improve cognition?
 
7. improve mood?
 
	
 
1. The primary endpoint risk of falling will be evaluated at 12 months
 
2. Number of falls in the groups
 
3. Number of injurious falls
 
4. Short Falls Efficacy Scale-International (Short FES-I) [49]
 
5. Berg Balance Scale (BBS) [50]
 
6. Montreal Cognitive Assessment (MoCA) [51]
 

	Objective	Endpoint
	8. improve health-related quality of life? 9. improve management of daily tasks? 10. induce identification and agreement with the intervention? 11. impact health-care utilization? 12. use of fall prevention recommendations. Estimation of motivational support. Tai Chi, EYT contamination in comparison groups. 13. Safety: Do EYT and Tai Chi induce harm? 14. Compliance	7. Geriatric Depression Scale (GDS-15) [52] 8. Health-related quality of life (SF-12) [53] 9. Self-maintaining and instrumental activities of daily living (IADL) [54] 10. Inner Correspondence/Peaceful Harmony with Practices (ICPH) [55] 11. Fragebogen zur Inanspruchnahme medizinischer und nicht-medizinischer Versorgungsleistungen im Alter (FIMA) [56]* 12. Self-designed questionnaire 13. Complications 14. Number of participated group sessions and number of days practiced at home

\* reduced to questions of doctors and specialists visits, therapies, inpatient or outpatient care, hospitalization, rehabilitation, surgery, medical aids, place of living.

## 2.2 Primary endpoint, definition of falls

The primary endpoint is chosen as the risk of falling, i.e. the fact if a patient falls at least once during a 6 months period or not. The time to first fall is used in the statistical analysis, calculated as time from handing out the study book to the first fall. For patients who do not fall within the 6 months observation period, the time to last contact will be used as censored observation. Death without previous fall will be regarded as competing event in the analysis. The secondary outcome number of falls is calculated as the number of falls recorded in the diary and ascertained by telephone visits. This will be analysed in relation to the individual follow-up time of the patients.

### Definition, classification

A fall is defined as “an unexpected event in which the participants come to rest on the ground, floor or lower level” [57].

An event is classified as a fall when the patient by accident, unintentionally lands on the floor or the ground, or fall and hit objects like stairs or pieces of furniture on a lower level. It is a rapid change from the upright/sitting position to the reclining or almost lengthened position [48, 57].

An event is not classified as a fall, if

- it is an intentional change to position to rest in furniture, wall or other objects, like lying down, sitting down, kneeling down;
- it is due to a syncope, seizure or another condition causing unconsciousness;
- it is a consequence of sustaining a violent blow or other violent impact;
- it is due to a sudden onset of paralysis as in stroke or an epileptic seizure;
- it is a sudden event of dizziness, uneasiness, vertigo or bumping into objects (e.g. furniture), without being accompanied by a fall (as defined above).

Frequency of falls will be self-reported daily in fall diaries and ascertained in monthly visits. Its assessments follows international guidelines [57].

### 2.3 Secondary endpoints

Risk of falling at 12 months will be defined as in 2.2 within 12 months.

Injurious falls (total number) are subdivided by “moderate” and “serious” [48]:

- 1) Moderate injurious falls are defined as those that resulted in sprains, bruises, scrapes, or joint injuries or if the individual needed medical care
- 2) Serious injurious falls are defined as those that resulted in a fracture, head injury, tendon rupture, or admission to a hospital (inpatient care), or that required stitches.

The BBS is a 14-item scale primarily assessing standing balance and sit-to-stand positions. Scores are based on a 5-point scale, rating from 0 to 4, based on performance quality and duration, or assistance needed. “0” indicates the lowest and “4” the highest level of function. The total score ranges from 0 to 56 points [50].

The MoCA is a brief cognitive screening tool for mild cognitive impairment and assesses several cognitive domains. The total sum score ranges from 0 to 30 and higher scores indicate higher functioning [51].

The Short FES-I is a 7-item questionnaire to measure fear of falling in elderly patients during different activities. It is to be filled out by the patient him/herself. Each item is rated on a four-point scale from 1 (not at all concerned) to 4 (very concerned). The total score ranges from 7 (no concern about falling) to 28 (severe concern about falling) [49].

The GDS-15 is a short, 15-item instrument, developed and validated for measurement of depressive symptoms among elderly people. It is to be filled out by the patient him/herself. Its items require a yes/no response. The total score ranges from 0 to 15. Sum scores 0-4 are considered normal, sum scores 12-15 indicate severe depression, in between as mildly depressed [52].

The SF-12 is a short-form generic measure of health status from the patient’s point of view. It is to be filled out by the patient him/herself. It contains 12 items on 8 health concepts. Results are expressed in terms of two meta-scores: Physical Component Summary and Mental Component Summary. Scores range from 0 to 100. Higher scores indicate better functioning. The mean score in a representative sample of the US population is 50 [53].

The IADL evaluates complex instrumental activities of daily living, on 8 items. The total score ranges from 0 to 8 in women, and from 0 to 5 in men [54].

The ICPH is a questionnaire to measure the Inner Correspondence/Peaceful Harmony with Practices (ICPH) of individuals with mind-body interventions. It is to be filled out by the patient him/herself. It contains 12 items, which are scored on a 5-point scale from disagreement to agreement. The total score ranges from 0 to 60. Scores >50 indicate higher agreement (positive attitude), scores <50 indicate disagreement (negative attitude) [55]. Only groups EYT and Tai Chi will perform this questionnaire.

FIMA is a generic questionnaire for the use of medical and non-medical services in old ages. It is to be filled out by the patient him/herself.

Medications are documented by the investigator. They are restricted to total number of drugs and to classes of fall risk increasing drugs (FRIDs), according to the list from the Swedish National Board of Health and Welfare:

- (increase fall risk) Opioids, Antipsychotics (lithium excluded), Anxiolytics, Hypnotics and sedatives, Antidepressants
- (may cause or worsen orthostatism) Vasodilators used in cardiac diseases, Antihypertensives, Diuretics, Beta blocking agents, Calcium channel blockers, Renin-angiotensin system inhibitors, Alpha-adrenoceptor antagonists, Dopaminergic agents, Antipsychotics (lithium excluded) Antidepressants

Herbal preparations, vitamins or homeopathic medicinal products are excluded.

Use of standard fall prevention measures, subjective estimation of motivational support; contamination with Tai Chi or EYT in non-Tai Chi and non-EYT groups, will be asked at month 6 only, using a self-designed questionnaire.

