#### 14.5.2 Secondary endpoints

For the analysis of the secondary endpoint total number of falls per patient within 6 months after handing out the study book, a negative binomial regression model will be used to test the efficacy of EYT versus Tai Chi versus standard care. Negative binomial is preferred over Poisson regression because of potential overdispersion. Fall rates for patients with follow-up times of less than 6 months will be adjusted by accounting for their exposure time. The model will include intervention type, study site, BBS score, and age as independent variables. Incidence rate ratios (IRR) between interventions will be calculated from the model with two-sided 95% CI. To take into account potentially present excess zeroes, a zero-inflated negative binomial model will be used as a sensitivity analysis

Other secondary endpoints will be analysed with appropriate regression models. Analyses will be repeated for the observation period of 12 months after date of handing out the study book. This also applies to the primary endpoint at 12 months.

As a sensitivity analysis these analyses above will be repeated in the PP.

Safety analyses will be performed in the SAF. Rates of complications will be calculated with two-sided 95% CI.

No formal interim analyses of the efficacy endpoints will be performed.

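### The ICPH score range of 0 to 60 cannot come from 12 five-point items, and the cut-off of 50 does not separate agreement from disagreement

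*Protocol*

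**What the plan says.** Protocol section 2.3 describes the instrument in two steps.

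- Items: "It contains 12 items, which are scored on a 5-point scale from disagreement to agreement". Numeric codes for the five categories are not given.
- Range and interpretation: "The total score ranges from 0 to 60. Scores >50 indicate higher agreement (positive attitude), scores <50 indicate disagreement (negative attitude"). No transformation of the sum is mentioned.

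The section adds: "Only groups EYT and Tai Chi will perform this questionnaire". The synopsis lists ICPH among the key secondary endpoints. In the table of section 2.1 it is the endpoint for secondary objective 10, which asks whether patients come to identify and agree with their intervention. On analysis, section 14.5.2 says only: "Other secondary endpoints will be analysed with appropriate regression models".

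**The concern.** The number of items, the response scale, the range and the cut-off all appear in one short paragraph and do not fit together. Two analysts could code the same forms differently, and each could cite the protocol for part of what they did.

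The interpretive sentence carries more risk than the range. A reader who applies it would report patients on the agreeing side of the scale as having a negative attitude. Objective 10 has no control-arm comparison, because standard care patients do not complete the questionnaire. The absolute level of the score, and hence its label, therefore carries much of the meaning.

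**Working it through.** **Inputs (protocol section 2.3).** ICPH: 12 items, 5 response categories, stated total 0 to 60, cut-off 50. Not stated: the item codes. Assumptions: the total is a plain sum, and the fourth category means 'agree', since the protocol names only the two ends of the scale.

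**Rule.** Range of a sum = number of items × lowest code, up to number of items × highest code.

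**The rule on other scales in the same section.**
- BBS: 14 × 0 = 0 to 14 × 4 = 56. Stated 0 to 56; reproduced.
- Short FES-I: 7 × 1 = 7 to 7 × 4 = 28. Stated 7 to 28; reproduced.

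**The rule on the ICPH.** The stated 0 to 60 is not reproduced by any run of five consecutive integer codes. It would need 60/12 = 5 points per item starting from 0. That means six codes (0-5), which is not a 5-point scale, or five categories spaced 5/4 = 1.25 apart.

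| Item codes | Possible total | All items neutral | All items in fourth category | What a score above 50 needs |
|---|---|---|---|---|
| 0 to 4 | 0 to 48 | 24 | 36 | cannot be reached |
| 1 to 5 | 12 to 60 | 36 | 48 | at least 3 items in the top category, the rest in the fourth |
| −2 to +2 | −24 to 24 | 0 | 12 | cannot be reached |
| 0 to 5 in steps of 1.25 | 0 to 60 | 30 | 45 | at least 5 items in the top category, the rest in the fourth |

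**The cut-off.** A total of 50 is an average item score of 50/12 = 4.17.
- Codes 0-4: the maximum is 48, so even a patient in the top category throughout falls below 50. All 24 scores above neutral (25 to 48) are labelled negative.
- Codes 1-5: with j items in the top category and the rest in the fourth, the total is 48 + j. So j = 0 gives 48 (negative), j = 2 gives exactly 50 (no class) and j = 3 gives 51 (positive). Of the 24 scores above neutral (37 to 60), 13 (37 to 49) are labelled negative, 1 is unassigned and 10 (51 to 60) are positive.
- Stated range 0 to 60, midpoint 30: of the 30 whole scores above the midpoint (31 to 60), 19 (31 to 49) are labelled negative, 1 is unassigned and 10 are positive.

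These are counts of score values, not of patients.

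**Where 50 would fit.** If the sum is rescaled as 100 × (sum − minimum)/(maximum − minimum), uniform neutral gives 50 and uniform fourth category gives 75, under either 0-4 or 1-5 coding. A cut at 50 then divides agreement from disagreement. The range and the cut-off may therefore refer to different scales. That is an inference from the arithmetic; the protocol does not say so.

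**The case against.** The best reply is that little hangs on the sentence. No section uses the cut-off to classify patients for a test, and a regression comparing mean ICPH between the two active arms does not need it. Item codes and scoring detail are often left to the SAP, which is not at hand. The first part stands and limits the size of the point. The second does not remove it: the protocol did not leave the scoring open but stated a range and a cut-off, and they are inconsistent with its own item description.

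Three stronger readings are tempting and are not supported.

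- A reader might infer that the cut-off is impossible under any coding. With codes 1-5 scores above 50 can be reached; there the cut-off is badly placed, not impossible.
- A reader might infer that ICPH is the one outcome on which EYT is expected to differ from Tai Chi. Section 1.1 lists several such outcomes, among them mood and quality of life, which GDS-15 and SF-12 cover.
- A reader might infer a companion error in the IADL, whose range depends on sex: "The total score ranges from 0 to 8 in women, and from 0 to 5 in men". Raw totals are indeed not comparable between women and men. But nothing in the protocol says that they are combined without regard to sex, and the handling of sex in that model is the kind of detail commonly left to the SAP.

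**Conclusion.** The point holds for the ICPH range and cut-off. The range of 0 to 60 is wrong for a sum of 12 five-point items with consecutive integer codes. The cut-off of 50 misclassifies on every raw scale the text could mean: everyone is negative under 0-4 coding, uniform 'agree' (48) is negative under 1-5 coding, and 31 to 49 is negative on the stated range. A score of exactly 50 has no class.

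The range error rests only on the stated item count and response scale, given a plain sum. The form that the mislabelling takes depends on the coding, which is not given. The consequence is confined to scoring and interpretation of one key secondary endpoint (objective 10) in two of the three arms. No figure for the primary endpoint, sample size, power or alpha depends on it.

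**What to change.** Rewrite the ICPH scoring text in section 2.3, after checking the instrument source that the protocol cites, so that it gives:

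1. the numeric code of each of the five categories;
2. the range and the cut-off on one scale: either the sum rescaled to 0-100 with 50 as midpoint, or the raw range with its own midpoint (24 on 0-48, 36 on 12-60);
3. the class of a score that falls exactly on the boundary.

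If the source defines a different threshold, state that threshold together with the scale it belongs to. The SAP should carry the same definition. The cost is a few sentences: no new data, no change to the questionnaire and no change to any planned comparison.

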### **Compliance:**

Compliance with group sessions is defined as participating in at least 70% of the group sessions.

Compliance with practicing at home is defined as practicing on average at least 70% of the recommended three times per week, irrespective of the duration.

Safety:

For details on definition and mode of analysis of complications see section 10.1.

---

### 3 Trial Plan

#### 3.1 Trial Design

Multi-centre, randomised controlled, open-label trial (1:1:1), stratified randomised by study site, with two active and one control parallel groups. The objective is to compare EYT, Tai Chi (each added to standard care) and standard care alone in elderly patients with chronic disease and increased risk for falling with respect to the risk of falling over a time period of 6 months (primary objective) and with respect to the number of falls, injurious falls, mobility, cognition, mood, quality of life, instrumental activities of daily living, fear of falling, health-care utilization, agreement with practices, use of fall prevention recommendations, estimation of motivational support, Tai Chi, EYT contamination in comparison groups and safety over a time period of 3, 6 and 12 months (secondary objectives).

#### 3.2 Treatment arms

Patients will be allocated 1:1:1 to EYT arm or Tai Chi arm or standard care alone arm (control). For details on treatment please refer to section 8.

#### 3.3 Treatment duration

Patients will be treated with EYT or Tai Chi for 6 months (month 1-3 twice per week, month 4-6 once per week). For details of premature termination see section 7. Standard care has no time limitation.

#### 3.4 Number of patients

A total of 550 patients will be randomised.

#### 3.5 Recruitment rate

The average recruitment rate is approximately 75 patient /quarter, starting quarter III 2019.

The recruitment capacity of the study sites for the complete trial is

Affiliation	Expected number of patients recruited for the complete trial
Freiburg University Hospital, Centre for Complementary Medicine	≥ 200

---

 for practical purposes the three groups will be referred to in this trial protocol as EYT, Tai Chi, and standard care alone, although standard care is present in all three groups

Tübingen University, Institute of General Practice and Interprofessional Care	100
University of Witten Herdecke	≥ 60
University of Essen, Klinik für Naturheilkunde und Integrative Medizin	≥ 60
Immanuel Hospital Berlin, Department of Internal and Complementary Medicine; Charité Berlin, Institute for Social Medicine, Epidemiology and Health Economics	60
Havelhöhe Hospital, Geriatrics, Berlin	45
Filderklinik, ARCIM Institute	30
Integrative Medicine, Ulm University Hospital	30

### 3.6 Timetable

Enrolment of first patient (FPFV)	3 rd quarter 2019
Enrolment of last patient	2nd quarter 2021
End of trial for last patient (LPLV)	2nd quarter 2022
Final statistical analysis	4th quarter 2022
Treatment duration per patient	6 months
Planned interim analysis	None

### 3.7 Participating Study Sites

Eight study sites are planned in Germany, which must meet the structural and personnel requirements for performing the planned regular study-related investigations.

If necessary, additional qualified study sites can be included in the performance of the study.

## 4 Trial Population and Selection Criteria

Trial population will be elderly patients with chronic disease and increased risk for falling.

A specific recruiting strategy will strengthen enrolment of patients which are economically disadvantaged, living a reclusive life.

*Inclusion criteria* are broad, reflecting the complex situation of chronic diseases and falls in aging patients and ensuring feasibility of recruitment and generalizability of the results. The criteria ensure to enrol patients in real need of therapy (i.e. clear increased fall risk and mobility impairment), but still having enough mobility to pursue the exercises and attend the classes and understand the logistics of the trial; the inclusion criteria also leave room for improvement of the condition if the intervention is successful:

The BBS, being a key inclusion criteria, is widely used to determine a patient's mobility and balance during a series of predetermined tasks [50] and is an appropriate tool to predict falls at a moderate accuracy level [58]. A BBS score of 49 combined with self-reported history of imbalance predicts a 50% risk of falls (2 falls within 6 months), with a specificity of 82% and a sensitivity of 91% [59]. That means, that a patient population with a BBS score of 49 or less (and history of imbalance) will have an at least 50% risk of falling within the next 6 months, indicating a clearly increased risk of falls [50, 59] and consecutively an indication for an intervention. This also refers to the "younger" part of the population of adults aged  $\geq 65$  years, as they can have an increased fall risk due to a chronic disease. A BBS score of 39 or less indicates a fall risk above 90%. In the range 54 to 46 a 1-point change in the BBS scores led to a 6% to 8% increase in fall risk [59]. Residents of a home for elderly that had an average BBS score of 48.3 (95% CI 47-49.6) used cane outdoors; elderly that had an average score of 45.3 (95% CI 44-46.5) used a cane also indoors [50].

*Exclusion criteria* shall ensure participation, the attendance of group sessions and follow-up visits: – "Visual, hearing or language problems affecting understanding of trial documents and procedures" will exclude patients that cannot comply with all trial requirements, understand informed consent, understand questionnaires, tests, diary documentation, etc. – "Medical conditions limiting participation", "Complete dependence on rollator", "Major cognitive impairment", "Severe personality disorder or psychiatric disease affecting group classes" will exclude patients who cannot participate in or benefit from group exercise classes. – "Life expectancy of less than 1 year" and "Permanent confinement to bed to be expected in less than a year" will exclude patients not to be expected to complete the trial. – "Participating in vigorous sports for exercise within last month" will exclude people already highly active, and less in need for an intervention. – "Participating in regular Tai Chi or EYT exercises currently or during the last 6 months" will exclude patients that will probably not benefit from the intervention as they already received it.

